2.2.5 Worst-case

A worst-case analysis visit will be created for parameters for which abnormalities and/or toxicity grades are defined to summarize values considered as the worst-case. Abnormalities are derived per parameter, and if both the lowest and the highest values

	Statistical Analysis Plan	
ARGX-113-2002	Final Analysis	Final 5.0 of 31Jan2025

are considered abnormal, then two worst-case analysis visits for the same parameter will be presented for the participant. For toxicity grades, the worst-case value of toxicity grades is associated with the highest toxicity grade and is derived per parameter and by toxicity direction (hypo/hyper).

All non-missing post-baseline values within the treatment and follow-up phase, including unscheduled assessments will be considered when deriving the worst-case analysis visit.

2.3 IMPUTATION AND ROUNDING RULES

2.3.1 *Missing values*

No missing values will be imputed (ie, observed cases analysis).

2.3.2 *Values below or above a threshold*

Laboratory safety and AChR-Ab values expressed as below/above the quantification limit (BLQ/ALQ) will be imputed by the value of the quantification limit itself. For total IgG, BLQ and ALQ values will not be imputed and will be excluded from the statistical analysis. For participants with a baseline PD value BLQ, the PD parameter will be excluded from the statistical analysis involving change and percent change from baseline. Listings will always show the non-imputed values.

PK concentrations BLQ will be flagged as such in the listings. For descriptive statistical analysis, all BLQ values will be set to zero. All ALQ values will be set to the upper limit of quantification for descriptive analysis. Listings will always present the original value.

2.3.3 *Rounding*

Variables will be rounded to the appropriate number of decimals at display level:

- Time since diagnosis and time between first administration in the study and the first administration of the cycle wherein the ICF for protocol v3.0 was signed will be rounded to 1 decimal.
- Estimated glomerular filtration will be rounded to 2 decimals
- Ratios will be rounded to the number of decimals of the parameter with the least number of decimals.
- Safety laboratory results will be rounded to a maximum of 3 decimal.

2.3.4 *Outliers*

There will be no outlier detection. All measured values will be included in the analyses.

2.4 PRESENTATION OF RESULTS

To support the J-MAA submission, all descriptive outputs (except for analysis by average treatment duration per year) described in this SAP will be repeated by region (Japanese / non-Japanese as defined in the study protocol). The definition of Japanese in the protocol is a participant whose parents and 4 grandparents are Japanese, who has Japanese nationality, was born in Japan, has not lived outside of Japan for a total

Statistical Analysis Plan

ARGX-113-2002

Final Analysis

Final 5.0 of 31Jan2025

of >10 years, and currently lives in Japan. Note that these additional outputs will be excluded from the FDA/EMA submission.

2.4.1 Calculation of descriptive statistics and percentages

For continuous variables, full descriptive statistics will only be presented if there are at least 2 non-missing observations. Alternatively, only the number of non-missing data points and mean are shown.

Descriptive statistics will include the number of non-missing data points, the arithmetic mean, the standard deviation (SD, for general and safety) or standard error (SE, for PD and efficacy), the median, minimum, Q1, Q3, and maximum. In addition, for PD and efficacy analyses, the 95% 2-sided confidence interval may be provided. For immunogenicity, geometric mean and geometric coefficient of variation (CV%) will be added.

The 95% 2-sided confidence interval, arithmetic mean, geometric mean, median, Q1, and Q3, will be presented with one more decimal place than the individual values. SE and SD will be presented with two more decimal places than the individual values. The minimum and maximum will be presented with the same number of decimal places as the individual values. CV% will be presented with 2 decimal places.

Descriptive statistics for PK concentrations will include n (number of observed values), arithmetic mean, SD, median, minimum and maximum, and CV%.

Serum concentrations will be presented with 3 significant digits in the original concentration units, except values ≥ 1000 , which will be rounded to an integer. The descriptive statistics should be rounded to the same number of significant digits as the individual values. If more than half of the values are BLQ, SD and CV% will not be calculated.

For event-type safety data, the number and percentage of participants with an event will be shown. The denominator will be all participants in the analysis set per treatment and cycle. All cycles will be shown, even if no events are present.

For frequency tabulations and cross-tabulations, the denominator will be all participants in the analysis set per treatment. For tables where results are shown by analysis visit, the denominator will be all participants in the analysis set per treatment and per analysis visit. Missing values will never be included in the denominator count when computing percentages. For cross-tabulations of post-baseline results versus baseline results, a ‘missing’ category will be shown for baseline results if applicable. Similarly for immunogenicity correlation tables, a “missing ADA/NAb classification” category will be shown if applicable.

2.4.2 Presentation of treatments

The following treatment labels will be used in the tables and listings:

- EFG SC (2001) – EFG SC
- EFG IV (2001) – EFG SC
- EFG IV (1705) – EFG SC
- TOTAL EFG IV – EFG SC
- TOTAL

SGS	Statistical Analysis Plan	
ARGX-113-2002	Final Analysis	Final 5.0 of 31Jan2025

2.4.3 *Presentation of treatment in modified safety analysis set*

After signing ICF for protocol version 3.0 (dated 2Feb2023), a subsequent treatment period can be administered at least 7 days after the last IMP administration of the previous cycle instead of 28 days, based on the clinical evaluation at the discretion of the investigator. Due to this protocol amendment, the number of injections per year can go up to 52 per year from year 2 onward, compared to 30 in year 1 of the study.

To evaluate the safety and efficacy across different groups with increased exposure, an additional participant classification will be created for the participants in the modified safety analysis set, based on their average weeks of treatment per year in the amended treatment + follow-up phase. Separate tables will be created for this “by average treatment duration per year” classification based upon the data since the cycle wherein the IC of the amended protocol was signed (ie, since the first amended cycle; see Table 2, section 2.2.1). All data will be listed, including the amended cycle number (where applicable).

For each participant, the average treatment duration per year will be calculated as follows:

- First, the number of completed cycles since the first amended cycle will be calculated.
- Completed cycles are cycles that were not cut off by study discontinuation or data cutoff date. For participants with a single (incomplete) cycle, the cycle will be considered a complete cycle in case the cycle duration up to data cutoff date is no less than 28 days.
- Based on these completed cycles, the total duration of completed cycles will be calculated as end date of last completed cycle – start date of first completed cycle + 1 day.
- The average treatment duration per year is then calculated as $365 * (\text{number of completed cycles}) / (\text{total duration of completed cycles}) * 4$.
- Based on the average treatment duration per year, participants are categorized as follows:
 - ≤ 30 weeks of treatment per year: these participants correspond to the participants with (on average) a cycle duration of at least 50 days.
 - > 30 to ≤ 38 weeks of treatment per year: these participants correspond to participants with shorter cycles, but not as short as (on average) weekly or nearly weekly treatment.
 - > 38 weeks of treatment per year: these participants correspond to the participants with shorter cycles, reflecting (on average) weekly or nearly weekly treatment.

	Statistical Analysis Plan	
ARGX-113-2002	Final Analysis	Final 5.0 of 31Jan2025

Tables by average treatment duration per year will not be shown by treatment group (in section 2.4.2), but by average treatment duration category only. The following labels will be used:

- <= 30 WEEKS OF TREATMENT/YEAR
- >30 to <=38 WEEKS OF TREATMENT/YEAR
- >38 WEEKS OF TREATMENT/YEAR
- TOTAL

The time (years) between first administration in the study and the first administration of the cycle wherein the ICF for protocol v3.0 was signed will be calculated as: (date of first administration of the cycle wherein the ICF for protocol v3.0 was signed - date of first administration in the study + 1 day)/365.25

2.4.4 *Cohorts*

Immunogenicity analyses will be performed on all participants included in the safety analysis set over the whole observation period, but also by cycle. Due to the difference in length of the observational periods, the number of participants will be different across cycles. The number of participants in the first cycle will be higher than the number of participants in the second cycle and so forth. To account for this attrition, cohorts of participants with at least 2 cycles, with least 3 cycles, etc. will be created. The analyses performed on the safety analysis set using all available data will be repeated for each of these cohorts to evaluate immunogenicity over cycles within similar cohorts. A cohort will need to contain at least 10 participants to be shown in the results (eg, if the total number of participants with at least 6 cycles is less than 10, data for this cohort will not be presented in the tables).

In tables by cycle, analyses will first be performed on the total safety analysis set using all available data (ie, cohort of all participants) and will then be repeated (as applicable) for each of these cohorts per cycle and, if applicable, for any cycle:

- Cohort of all participants
 - Cycle 1
 - Cycle 2
 - Cycle 3
 - Etc.
 - Any cycle (in cohort up to cycle n)
- Cohort of participants with at least 2 cycles
 - Cycle 1
 - Cycle 2
 - Any cycle (ie, Cycle 1 or cycle 2)
- Etc.

2.4.5 *Ordering in tables, figures and listings*

For presentations by analysis visits, IP0 visits will not be considered in the tables.

All tables will be presented per treatment and cycle unless specified otherwise. If present, the worst-case will be shown last. Cycles will be indicated as a subtitle or

	Statistical Analysis Plan	
ARGX-113-2002	Final Analysis	Final 5.0 of 31Jan2025

within the table like “Cycle n”. A selection of results will also be presented by cohort (‘cohort of participants with at least x cycles’; see section 2.4.4). A cohort should contain at least 10 participants to be shown.

Listings for general characteristics, results will be ordered by treatment labels (as defined above) and patient, unless specified otherwise.

All other listings will be ordered by treatment, patient, period, analysis visit and time point, unless specified otherwise.

In tables showing several parameters, each parameter will begin on a new page and parameters will be sorted alphabetically, within the parameter category if applicable.

The ordering of groups will be done as shown in section 2.4.2.

3. GENERAL CHARACTERISTICS ANALYSES

3.1 SUBJECT DISPOSITION

The following patient data will be tabulated:

- The number of participants in each analysis set.
- The number and percentage of participants by country and investigator.
- The number and percentage of participants for each period/analysis visit.
- The number and percentage of participants for each period with on-site and phone call visits.
- Descriptive statistics of the cycle duration (see section 2.2.1), calculated as cycle end date – cycle start date + 1 day. Frequency tabulation of the cycle duration in weeks.
- Descriptive statistics of the study duration and of each analysis phase. Study duration is calculated as study end date (date of last contact) – study start date (date of informed consent) + 1 day. Data for ongoing participants are censored at the cutoff date for interim analysis. Analysis phases are defined in section 2.2.1.
- The number and percentage of participants who completed or discontinued the study as documented on the study termination page and the number and percentage of participants for each study discontinuation reason.
- The number and percentage of participants who completed or discontinued the study as documented on the study termination page and the number and percentage of participants for each study discontinuation reason by cycle.
- The number and percentage of participants who completed or discontinued the treatment as documented at the end of the treatment page and the number and percentage of participants for each treatment discontinuation reason.
- The number and percentage of participants who completed or discontinued the treatment as documented at the end of the treatment page and the number and percentage of participants for each treatment discontinuation reason by cycle.
- Frequency tabulation of the treatment and follow-up duration per 6-monthly category, showing the number and percentage in each category and additionally cumulative number and percentages. Categories are defined as follows: <6 months (< 168 days); 6 to <12 months (168 - 350 days); 12 to <18 months (351 - 532 days); 18 to <24 months (533-715 days); 24 to <30 months (716-897 days); 30 to <36 months (898 - 1080 days); 36 to <42 months (1081-1263 days); 42 to <48 months (1264 - 1445 days).

Additionally, the following patient data will be provided by average treatment duration per year:

- The number and percentage of participants by country and investigator.
- Descriptive statistics of the cycle duration (see section 2.2.1), calculated as cycle end date – cycle start date + 1 day. Frequency tabulation of the cycle duration in weeks.

SGS	Statistical Analysis Plan	
ARGX-113-2002	Final Analysis	Final 5.0 of 31Jan2025

- The number and percentage of participants who completed or discontinued the study as documented on the study termination page and the number and percentage of participants for each study discontinuation reason.
- The number and percentage of participants who completed or discontinued the study as documented on the study termination page and the number and percentage of participants for each study discontinuation reason by cycle.
- The number and percentage of participants who completed or discontinued the treatment as documented at the end of the treatment page and the number and percentage of participants for each treatment discontinuation reason.
- The number and percentage of participants who completed or discontinued the treatment as documented at the end of the treatment page and the number and percentage of participants for each treatment discontinuation reason by cycle.
- Frequency tabulation of the treatment and follow-up duration per 6-monthly category, showing the number and percentage in each category and additionally cumulative number and percentages.
- Frequency tabulation of the cycle wherein the ICF for protocol v3.0 was signed.

All information collected in the CRF concerning study and treatment discontinuation will be listed, including information related to discontinuation during IP0. Listings with all COVID-19-related comments and COVID-19-related remote visits will also be prepared.

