 - If a participant enters year 2 of the study during a TP, the remaining TP visits and subsequent IP_nV1 must be completed according to the Year 1 SoA (refer to [Table 1](#)).
- intertreatment period (IP):
 - Year 1: at least 28 days between TPs
 - Year 2 onward: recommended to have IPs of at least 28 days, but a subsequent TP can be administered earlier based on clinical evaluation at the discretion of the investigator. A minimal interval of 7 days after the last IMP administration of previous cycle must be maintained.

Eligible participants will enter the study on their last visit of the antecedent study, ARGX-113-2001 or ARGX-113-1705. If they are in need of retreatment, the participants will start with a TP. A TP will consist of an injection of efgartigimod PH20 SC 1000 mg q7d for a total of 4 injections. If the participants are not in need of retreatment, they will start with an IP (visit IP₀V1). Participants or their caregivers will be trained to perform the injection and will be allowed to perform the injection when they are competent to do so. Caregiver-supported or

[figure not shown]
self-administration can be performed at the site or at home, based on the participant's preference. Participants will be discontinued from the study if it is in their best interest, as determined by the investigator or sponsor.

Participants will remain in the study for at least 1 year, until efgartigimod PH20 SC becomes commercially available, available through another continued access program for gMG, or until 31 Dec 2024, whichever comes first.

Data Monitoring/Other Committee: Yes (see Section [10.1.5.1](#))

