Amended Treatment + Follow-up	Amended cycle 1	First injection date/time of the cycle wherein the ICF for protocol v3.0 was signed ^b	First injection date/time in next cycle – 1 minute or if last cycle: date of last contact ^a , with 23:59 added as time part
	Amended cycle n	First injection date/time in cycle n	First injection date/time in next cycle – 1 minute or if last cycle: date of last contact ^a , with 23:59 added as time part
	Amended cycle x	First injection date/time in cycle x	Date of last contact ^a , with 23:59 added as time part

^a Date of interim cutoff for ongoing participants

^b If participant signed ICF for protocol v3.0 multiple times, the first date of signature will be used.

AEs and concomitant medications will be allocated to phases and periods as described in sections 5.1.2 and 3.5.2 respectively. All other assessments will be allocated to phases and periods based on the assessment date/time.

In case of (partially) missing date/time fields disabling allocation or date(time) equal to dosing date(time), information from visit label and protocol SoA will be used to allocate to the correct phase and period. If this is not possible, assessments will be

allocated to the first possible cycle unless the available parts of the assessments start or stop date/time provide evidence the assessments did not occur during that period.

In addition and to complement the analyses by cycle, a set of phases will be derived for analyses of adverse events over time (by 3-monthly periods) (see Table 3), independent of cycles of treatment.

Table 3: Phase definition by 3-monthly periods

Phase	Start	End
(Amended) 0-3 Months	First injection date/time in (amended) cycle 1	Minimum of (First injection date in (amended) cycle 1 + 90 days, date of last contact ^a), with 23:59 added as time part
(Amended) 4-6 Months	End date/time of Phase 0-3 Months + 1 minute	Minimum of (First injection date in (amended) cycle 1 + 180 days, date of last contact ^a), with 23:59 added as time part
(Amended) $n^*3-2 - n^*3$ Months ($n \geq 3$)	End date/time of previous phase + 1 minute	Minimum of (First injection date in (amended) cycle 1 + n^*90 days, date of last contact ^a), with 23:59 added as time part

Where n is 3 for the third 3-monthly period, 4 for the fourth, etc.

^a Date of last contact or cutoff date of interim analysis for participants ongoing in study 2002, whichever is earlier

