3.5 PRIOR AND CONCOMITANT THERAPIES

3.5.1 *Available data*

All therapies are coded using the September 2021 version of the WHO-DRUG. ATC selection is performed. ATC coding up to level 4 is available in the clinical database. For each therapy, a start date or prior flag and stop date or ongoing flag are collected.

3.5.2 *Derivation rules*

Based on their start and stop date, therapies will be allocated to each analysis period during which they were administered. A therapy can therefore be reported in more than one analysis period.

Analysis periods are defined in section 2.2.1. Therapies with (partially) missing dates will be allocated to each period unless the available parts of the therapy start or stop date or prior and ongoing flags provide evidence the therapy was not taken during that period.

Concomitant therapies are defined as therapies taken on or after the first OLE dose date. Prior therapies are not in the scope of this interim analysis.

MG-specific therapies that were administered during the first year will be considered separately. First year is defined as the period starting from first dose in study 2002 until day 365 relative to first dose.

3.5.3 *Presentation of results*

Concomitant therapies will be tabulated, by ATC class (level 1 and level 3) and generic term. This table will be provided overall, not by cycle. The table for concomitant therapies will include MG therapies.

All concomitant therapies data will be listed with detailed information about ATC classes. Concomitant procedures will be listed separately.

For MG therapies during the first year, the number of participants per medication class (steroids, NSIDs and AChE inhibitors: appendix 9.3) and the combination of classes will be shown.

A separate listing will be created of participants receiving rescue medications. Rescue medications will be identified based on a flag on the SDTM data in the CM domain (Concomitant Medications).

Vaccination history will only be listed.

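### SAP 3.1 starts each 6-monthly duration category 14 to 15 days before the month on its label, so counts of participants followed for at least 6, 12, 18 or 24 months can only be too high or unchanged

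*SAP*

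**What the plan says.** SAP 3.1 (Subject disposition) plans a frequency table of treatment and follow-up duration per 6-monthly category, "showing the number and percentage in each category and additionally cumulative number and percentages". The day ranges are printed beside the labels: "<6 months (< 168 days); 6 to <12 months (168 - 350 days); 12 to <18 months (351 - 532 days", then "18 to <24 months (533-715 days); 24 to <30 months (716-897 days", then 898 to 1080 days for 30 to <36 months, then "36 to <42 months (1081-1263 days); 42 to <48 months (1264 - 1445 days". The output is Table 14.1.1.10 on the safety analysis set. Table 14.1.1.10B repeats it on the modified safety analysis set by average treatment duration per year. SAP 3.1 does not restate the bounds for that repeat, so I assume that they are the same.

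No reason is given for the cut-points: no visit-window tolerance and no rounding rule. SAP 2.3.3 rounds variables at display level and does not mention rounding before categorisation.

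Elsewhere the SAP measures a year in the usual way. Section 3.5.2: "First year is defined as the period starting from first dose in study 2002 until day 365 relative to first dose". Section 2.4.3 converts to years with "date of first administration in the study + 1 day)/365.25".

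**The concern.** A label of the form 12 to <18 months tells the reader that everyone in the category has at least 12 months. Here the category opens at day 351, which is short of 12 months on any calendar convention. The same holds for every other threshold.

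The study's primary objective is long-term safety, and these two tables are the planned display of how many participants reached each duration. Anyone who quotes a count by its month label will not see the day range behind it. The error in such a count runs one way, towards longer follow-up.

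**Working it through.** **Inputs.** Lower bounds from SAP 3.1: 168, 351, 533, 716, 898, 1081, 1264. The last category ends at 1445, so the next bound would be 1446. Year length of 365.25 days from SAP 2.4.3. Maximum enrolment of 201 from SAP 1.3.

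**Step 1: reproduce the SAP's bounds.** One month is 365.25/12 = 30.4375 days. For a label of k months, compute (k − 0.5) × 30.4375 and round up to a whole day.

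**Step 2: compute the labelled months.** Compute k × 30.4375, subtract the SAP bound to get the gap, and round up to get the first whole day that satisfies the label.

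| k (months) | (k − 0.5) × 30.4375 | Rounded up | SAP bound | k × 30.4375 | Gap (days) | First day that satisfies the label |
|---|---|---|---|---|---|---|
| 6 | 167.41 | 168 | 168 | 182.63 | 14.6 | 183 |
| 12 | 350.03 | 351 | 351 | 365.25 | 14.3 | 366 |
| 18 | 532.66 | 533 | 533 | 547.88 | 14.9 | 548 |
| 24 | 715.28 | 716 | 716 | 730.50 | 14.5 | 731 |
| 30 | 897.91 | 898 | 898 | 913.13 | 15.1 | 914 |
| 36 | 1080.53 | 1081 | 1081 | 1095.75 | 14.8 | 1096 |
| 42 | 1263.16 | 1264 | 1264 | 1278.38 | 14.4 | 1279 |
| 48 | 1445.78 | 1446 | 1446 (implied) | 1461.00 | 15.0 | 1461 |

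All eight bounds match. The bands have the right width (182 or 183 days); only their starting point is shifted, by half a month. That is the effect of rounding to the nearest month and then attaching labels meant for completed months.

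**Step 3: check that the year convention does not matter.** SAP 2.4.3 also uses 365 when it annualises treatment. With a 365-day year the thresholds are 182.5, 365, 547.5, 730, 912.5, 1095 and 1277.5, and the gaps are 13.5 to 14.5 days. The band misclassified at 12 months is then 351 to 364 days instead of 351 to 365.

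**Step 4: direction.** A participant in a misclassified band is moved up one category, never down. The number at or above a threshold is therefore too high by the number of participants in the band just below it, or unchanged if that band is empty. SAP 3.1 does not say which way the table cumulates. If it cumulates upward, the same participants are missing from the count with short follow-up. A single middle category can err either way, because it gains at its lower edge and loses at its upper edge.

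**Step 5: size.** Assume 201 durations spread evenly over 1 to 1445 days and a band of about 14.5 days: 201 × 14.5/1445 = 2.0 participants per threshold. The possible range is 0 to everyone whose duration falls in the band.

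**The case against.** The strongest reply is that this is a disclosed convention. The day ranges are printed, the bands are contiguous and equally wide, and a consistent rule reproduces them. That is fair as an explanation of where the numbers come from, but printing the ranges does not make the labels true, and the rule itself is not stated. A reader of the table will quote months.

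Several stronger readings are tempting, and the documents do not support them.

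- **The SAP's 3-monthly adverse-event phases contradict the bounds throughout.** Table 3 in SAP 2.2.1 ends its second phase at "Minimum of (First injection date in (amended) cycle 1 + 180 days, date of last contact", so it counts 30 days per month. Against that clock the bounds are 12 days early at 6 months, 9 at 12 months and 4 at 24 months, but 1 day late at 36 months (1081 against 1080) and 4 days late at 42 months (1264 against 1260). Table 3 also serves a different purpose.
- **Exits cluster at the thresholds.** A reader might infer a peak near 2 years from the day-730 visit in SAP Appendix 9.4.1. The current protocol has no 2-year exit, and that appendix schedule still describes a 2-year study. At 1 year, Protocol 1.1 says "Participants will remain in the study for at least 1 year", which is a minimum and not an exit date. Someone with a short lead-in before the first injection who left at exactly 1 year would fall in the band, but nothing shows that this is common.
- **About 8% of participants are misclassified.** The figure 15/183 is a share of one 6-month band under an even spread. It is not the error in a cumulative count.
- **The exposure basis of the safety analysis is inflated.** Event rates in SAP 5.1.2 use summed follow-up time, and SAP 3.1 also plans descriptive statistics of study and phase duration. Neither uses these categories.

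**Conclusion.** The bounds are wrong for the labels they carry. Each precedes its labelled month by 14 to 15 days on a 365.25-day year, and the 12-month bound of 351 conflicts with the SAP's own first year. The direction is certain; the size is not. It is about 2 participants per threshold under the even-spread assumption with the maximum of 201 participants, and could be none. Table 14.1.1.10B covers a subset, so its absolute numbers can be no larger if durations there are counted on the same clock.

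The consequence is confined to Tables 14.1.1.10 and 14.1.1.10B, which are descriptive. It is a small error in a figure that bears directly on the study's purpose and is cheap to correct. The check treats duration as whole days counted inclusively, as SAP 3.1 does for study duration; the SAP gives no separate formula for the duration used in these tables.

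**What to change.** Classify unrounded duration in days with one convention, the 365.25-day year of SAP 2.4.3:

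- <6 months: <183 days
- 6 to <12 months: 183 to 365
- 12 to <18 months: 366 to 547
- 18 to <24 months: 548 to 730
- 24 to <30 months: 731 to 913
- 30 to <36 months: 914 to 1095
- 36 to <42 months: 1096 to 1278
- 42 to <48 months: 1279 to 1460

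Apply these in both tables, and state in the table which way the cumulation runs.

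The cost is one line in SAP 3.1 and one format used by two tables. The long-follow-up counts become slightly less favourable or stay the same. Interim analyses were performed under separate SAPs (SAP 1.5), and the list of changes from version 4.0 in SAP 6.3 does not mention these categories, so they may have been carried over. If interim tables used the old bands, a footnote on the changed cut-points is needed for comparability. If the sponsor prefers to keep the current bounds, the least that is needed is to state the rounding rule in SAP 3.1 and in a footnote to both tables.
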